11. PHARMACOKINETIC / PHARMACODYNAMIC ANALYSES

11.1. Exposure-Response for Efficacy and Safety Endpoints

If deemed appropriate and if data permit, exposure-response relationships between belantamab mafodotin exposure (e.g., dose, dose intensity, concentration, Cmax, or AUC) and clinical activity and/or toxicity (e.g., response, corneal event, AESIs) may be explored using population methods. If data permit, the effects of covariates may be explored. Details of these analyses will be reported under a separate RAP, and the results of this analysis will be provided in a separate report.

[figure not shown]
11.2. Concentration-QTc Analyses

For each ECG assessment, the individual participant's QTcF change from baseline will be calculated and will be merged with time-matched PK concentration values for the timepoints at which they are available. QTcF change from baseline (y-axis) will be plotted against the PK concentration data (x-axis) separately for each analyte (ADC, total mAb, and cys-mc-MMAF). If appropriate, linear regression analyses may be performed for each analyte- Δ QTcF plot.

CONFIDENTIAL

208465

CCI

14. APPENDICES

14.1. Appendix 1: Exclusions from Per Protocol Population

This study does not have per protocol population.

14.2. Appendix 2: Schedule of Activities

Study Assessments	Screen n ¹	Cycle 1 Day 1 ²	Cycle 1 Day 2	Cycle 1 Day 4	Cycle 1 Day 8	Cycle 1 Day 15	Treatment Period ³ Cycle = 21 days	End of Treatment Follow-up ⁴	PD Follow-up ⁵
							D1 of C2 - CX		
Informed Consent	X								
Baseline Demographics	X								
Medical History including disease history and characteristics	X								
Physical Exam	X	X					X every 3 weeks	X	X
Safety									
Ocular Exam	X ⁶						X ⁷	X ⁷	X ⁸
ECOG Performance Status	X						X every 3 weeks	X	
Vital Signs (BP, HR, Body Temperature) ^{9, 10}	X	X			X	X	X	X	
Weight ⁹ and Height	X	Weight only					Weight only	Weight only	
Hematology ¹¹	X	X		X	X	X	X every 3 weeks	X	
Clinical chemistry ¹¹	X	X	X	X	X	X	X every 3 weeks	X	X ¹¹
Urine Dipstick ¹¹	X	X					X every 3 weeks	X	X
eGFR (by MDRD formula- see Appendix 8)	X	X					X every 3 weeks	X	
Spot urine for creatinine/albumin ratio ¹²	X	X					Cycle: 3, 5, 7 and Every other cycle thereafter	X	
CRP	X						X every 3 weeks	X	
HBsAg, HBcAb, and hepatitis C Ab. ¹³	X								
Troponin I ¹⁴	X								
BNP ¹⁵	X								
Pregnancy Test ^{9, 16}	X	X					X	X	X ¹⁶
ECHO ¹⁷	X						as clinically indicated		
12-lead ECG ^{9, 18}	X	X ¹⁸	X ¹⁸	X ¹⁸	X ¹⁸	X ¹⁸	X.	X	
PK and ADA									
PK ¹⁹		X ¹⁹	X ¹⁹	X ¹⁹	X ¹⁹	X ¹⁹	X ¹⁹	X ²⁰	
ADA ²¹		X ²¹					X ²¹	X ²¹	
Disease Evaluation									
β ₂ Microglobulin	X								
Response assessment ²²							X every 3 weeks	X ²³	X
Skeletal survey ²⁴	X						As clinically indicated ²⁵		
Imaging for Extramedullary disease ²⁶	X						C5, C9, C13 and C17, every 12 weeks then as clinically indicated ²⁶	X ²⁷	X
UPEP (Urine Protein Electrophoresis) 24 hr urine collection	X						X every 3 weeks	X	X
Urine Immunofixation	X						At time of first achieving CR or suspected PD after CR or sCR	At time of first achieving CR or suspected PD after CR or sCR	At time of first achieving CR or suspected PD after CR or sCR

Study Assessments	Screen n ¹	Cycle 1 Day 1 ²	Cycle 1 Day 2	Cycle 1 Day 4	Cycle 1 Day 8	Cycle 1 Day 15	Treatment Period ³ Cycle = 21 days	End of Treatment Follow-up ⁴	PD Follow-up ⁵
							D1 of C2 - CX		
SPEP (Serum Protein Electrophoresis)	X						X every 3 weeks	X	X
Serum immunofixation	X						At time of CR or suspected PD after CR or sCR	At time of CR or suspected PD after CR or sCR	At time of CR or suspected PD after CR or sCR
Serum Kappa, lambda free LC, FLC ratio	X						X every 3 weeks	X	X
Calcium corrected for albumin (serum)	X						X every 3 weeks	X	X
IgG, IgM, IgA	X	X					X every 3 weeks	X	X
IgD/E ²⁸	X	X					X every 3 weeks	X	X
Bone Marrow Aspiration / biopsy									
FISH testing on bone marrow ²⁹	X								
CCI									
BM for disease assessment ³¹	X						At the time of CR (always) or at time of suspected PD (only if not evident otherwise)	Only if CR has been achieved by this visit, or suspected PD not evident otherwise	Only if CR has been achieved by this visit, or suspected PD not evident otherwise
Bone marrow to assess sCR by (IHC) ³²							X ³²	Only if CR has been achieved on this visit.	Only if CR have been achieved on this visit
Biomarker									
CCI									
Study treatment									
Premedication if needed		X					X		
Belantamab mafodotin administration ³⁴		X					X		
Preservative-free artificial tears ³⁵		X					Everyday until end of Study treatment		
Adverse Events ³⁶	X	X	X	X	X		X		
Concomitant Medications	X	X	X		X	X	X		
Health Outcomes									
OSDI ³⁷	X	X				X every 3 weeks	X	X	

Abbreviations:

ADA = Anti-drug Antibody; ALP = alkaline phosphatase; BM = bone marrow; BNP = B-type natriuretic peptide; BP = blood pressure; C1D1 = Cycle 1 Day 1, etc.; CK = creatine kinase; CRP = C-reactive protein; EM = extramedullary; EOI = End of Infusion; FISH = fluorescence in situ hybridization; FLC = free light chain; HR= heart rate; Ig = immunoglobulin; PK = Pharmacokinetics; QID = 4 times a day; SOI = start of infusion; SPEP = serum protein electrophoresis; UPEP = urine protein electrophoresis; OSDI = Ocular Surface Disease Index.

1. All Screening assessments must be performed within 21 days prior to first dose unless otherwise specified. Informed Consent must be signed before any study-specific assessments are performed. Screening Assessment do not need to be repeated on C1D1 unless otherwise specified.
2. Assessments scheduled on days of dosing must be done prior to drug administration, unless otherwise specified. All other assessments can be done ± 3 days unless otherwise specified.
3. Belantamab mafodotin will be administered intravenously on Day 1 (D1) of every 21-day cycle until disease progression, death, unacceptable toxicity, withdrawal of consent or end of study.
4. The End of treatment (EOT) follow-up visit is to assess any residual AEs or toxicities associated with Study treatment. The visit should occur -within 45 days after last dose or before the start any new anti-cancer therapy.
5. PD follow-up once every 21 days: Participants who discontinue IP for a reason other than PD, disease evaluations will continue to be performed once every 21 days (± 7 days) until confirmed PD, death, start of a new anticancer treatment, withdrawal of consent, or end of the study whichever occurs first.
6. Screening examination will be performed by an ophthalmologist (or an optometrist if an ophthalmologist is not available) within 21 days prior to first dose. See Protocol Section 8.3.9 for the list of ophthalmic exam procedures.
7. On-study ophthalmic exams to be performed by an ophthalmologist (or an optometrist if an ophthalmologist is not available) pre-dose every 3 weeks (schedule of assessment window should be within 5 days prior to dosing, all efforts should be made to schedule as close to dosing as possible). After the 6th dose of belantamab mafodotin (no schedule of assessment window needed): If there are no significant (Grade 2 or above) ocular symptoms or vision changes the frequency of ophthalmologic exams may be decreased to every 3 months until

end of treatment. In case of persistent ocular exam findings, newly developed ocular symptoms or vision changes, further ocular exams should be performed at least every cycle until resolution (to Grade 1 or baseline) or more frequently as clinically indicated by the qualified eye care specialist(Protocol Appendix 9). See Protocol Section 8.3.9 for the list of ophthalmic exam procedures.

8. Additional exams may be performed by the ophthalmologist (an optometrist if an ophthalmologist is not available), as clinically indicated.
9. If a participant's belantamab mafodotin dose is not administered at a given visit, the following activities do not need to be performed at that visit unless clinically indicated: ECG, weight, vitals, pregnancy test. Please follow the visit schedule in the SOA above, and perform these activities prior to a belantamab mafodotin infusion.
10. On initial (first infusion) dosing day, vital signs must be assessed at pre-dose (within 30 minutes prior to start of infusion(SOI)), +10 minutes after SOI, end of infusion (EOI), and 1 hour post EOI. On subsequent dosing days, vital signs must be assessed at pre-dose (within 30 minutes prior to SOI), and at EOI. On days where vital sign time points align with PK sampling time points, vital signs must be assessed prior to PK samples being drawn. On days where vital signs are measured multiple times, temperature does not need to be repeated unless clinically indicated.
11. Refer to Protocol Table 9 for a comprehensive list of lab tests that must be collected for all participants. If labs are completed within 72 hours prior to the first dose, this assessment need not be repeated on Day 1 of Cycle 1. Creatinine only is required at PD visits (not a full chemistry).
12. Creatinine / albumin ratios (spot urine from first void) at screening and C1, C3, C5, C7 and every other cycle thereafter (local labs or central if local not available).
13. Hepatitis: If the participant is hepatitis C virus (HCV) positive by serology, an additional Hep C RNA testing may be done to determine participant eligibility (if negative- participant is eligible).
14. Troponin I will be measured at the local lab or by central laboratory if not available locally. If cardiac workup is required due to safety concerns during the study, troponin must be measured.
15. B-type natriuretic peptide (BNP) to be measured locally, or by a central laboratory if not available locally, at screening; if cardiac workup is required due to safety concerns during the study, BNP must be measured.
16. Perform only in women of childbearing potential. A serum pregnancy test must be performed at screening, and subsequent pregnancy tests may be either serum or urine. If test is completed within 72 hours prior to the first dose, this assessment need not be repeated on Day 1 of Cycle 1.
For questionable cases, follicle stimulating hormone (FSH) and estradiol (as needed in women of non-child bearing potential only) should be performed at local lab. See Protocol Section 5.1, Section 8.3.5, and [Appendix 4](#) for more details.
 - a. Final pregnancy test (serum or urine) must be performed in women of childbearing potential at the EOT Visit, and 8 months after the last dose of study treatment may be via a urine pregnancy test kit mailed to the participant's home with results reported by telephone.
17. Echocardiography for LVEF performed within 3 months of screening are acceptable as screening value. For participants with an abnormal LVEF (per institutional standards), the participant is to follow-up with a cardiologist.
18. ECGs on dosing days: Triplicate ECGs to be performed at pre-dose (within 30 minutes prior to SOI) and EOI at cycle 1. Triplicate ECGs should be collected prior to PK sample on Cycle 1 Day 2, Day 4, Day 8 and Cycle 1 Day 15. Single ECG at screening, at all other cycles, and End of Study Treatment On days where ECG time points align with PK sampling time points, ECGs must be performed within 30 minutes prior to PK samples being drawn (PK sample must be taken at the exact nominal time). ECGs will be collected and stored at site. See SRM for details on collection regarding ECGs.
19. PK samples to be taken in all participants for belantamab mafodotin ADC, total antibody and cys-mcMMAF measurements on:
 - C1D1 at pre-dose (within 30 minutes prior to SOI), at the end of infusion (EOI) (+5 min), 2 h post-SOI (± 15 min), 4 h post-SOI (± 15 min), 8 h post-SOI (± 1 h), 24 h post-SOI (± 2 h);
 - C1D4 anytime (± 1 day);
 - C1D8 anytime (± 1 day);
 - C1D15 anytime (± 1 day);
 - C1D22 anytime (± 1 day) (collect one PK sample only if the dose for the next cycle is delayed; this sample will be combined)
 - For C2D1, C4D1, C6D1, C9D1, and C12D1, collect samples at pre-dose (within 30 min prior to SOI) and at the EOI (+5 min);
 - For every six cycles after C12 (e.g., C18, C24, etc.), collect one sample at pre-dose (within 30 min prior to SOI). However, one year after the first dose of last subject, PK samples will only be collected for the interpretation of ADA results in the following visits.
20. Collect 1 PK sample at each participant's final visit.
21. All ADA samples will be collected prior to each infusion at C1, C2, C4, C6, C9, C12, and every 6 cycles thereafter (C18, C24, etc.) until end of treatment (dosing days only) and at the last visit.
22. Disease Response Assessment: Response assessment must be conducted Q3W based on standard disease laboratory tests (serum and urine M protein test, FLC, IgD/E, if applicable), Ca corrected for albumin, bone marrow aspirate (in case of CR, or suspected PD if not evident otherwise). Assessment based on imaging has to be included in participants with extramedullary disease at indicated time points. Response evaluation will be performed according to the IMWG Uniform Response Criteria for Multiple Myeloma 2016.
23. For participants who are discontinuing IP due to PD the confirmation must be performed on a different date from a different blood collection within 14 days of the original disease progression. This may be performed at the EOT follow-up visit.
24. Skeletal Survey: Imaging of bones for lytic lesions by a method aligned with the institutional guidance (X-ray, CT, or [Computed tomography], or MRI [Magnetic resonance imaging]). Skeletal survey results within 30 days prior to C1D1 are acceptable.
25. Only if clinically indicated or if worsening clinical symptoms suggest PD.
26. Imaging is only required for participants with extramedullary disease (CT, MRI, or PET [Positron Emission Tomography]/CT can be applied per local guidance). Screening assessment may be performed up to 30 days prior to C1D1. The same modality should be used throughout the study (i.e., if PET scan was used as baseline, participant needs to be followed by PET scans). Plasmacytoma measurements should be taken from the CT portion of the PET/CT, or MRI scans, or dedicated CT scans where applicable. For participants with skin only involvement, skin lesions should be measured with a ruler. Measurement of tumor size will be determined by the Sum of the Products of the maximal perpendicular diameters of measured lesions (SPD). Evaluations should be performed by the same method as at screening.
27. In participants with extramedullary MM, if the last radiographic assessment occurred ≥ 8 weeks prior to the participant's withdrawal from study treatment, and progressive disease has NOT been documented –then a new assessment (presence or absence extramedullary disease) should be obtained at the time the participants withdrew from study treatment.
28. Only required for participants with IgD/E myeloma, where serum m-component cannot be followed otherwise
29. FISH testing at least for: t (4;14), t (14;16), 17p13del, and +1q21. FISH results from samples taken within 60 days prior to first dose are acceptable. If this cannot be performed at a local lab the samples can be sent to the central lab

30. **CCI**

31. Bone Marrow for disease assessment performed within 14 days prior to first dose is acceptable.
32. Bone marrow biopsy for IHC to confirm sCR after achieving a CR.

33. **CCI**

34. Belantamab mafodotin administration: Study drug administration \pm 3-day window.
35. Corneal management information:
a. Prophylactic preservative-free artificial tears must be administered in each eye at least 4-8 times daily beginning on Cycle 1 Day 1 until end of treatment.
b. At the start of each infusion, participants may apply cooling eye masks to their eyes for approximately 1 hour or as long as tolerated.
36. All related SAEs are to be collected from consent through PD follow-up.
37. Additional assessments may be conducted for those participants who experience a worsening in visual function. Participants who discontinue participation in the study will continue to be assessed during follow-up until resolution of visual symptoms. Continue to follow up with participants via telephone who are still experiencing visual symptoms even after discontinuation

14.3. Appendix 3: Assessment Windows

All assessments on study must be performed on a calendar schedule in [Appendix 2: Schedule of Activities](#) and must not be affected by dose interruptions/delays. For post-baseline assessments, a window of ± 3 days is permitted to allow for flexible scheduling, and PD follow-up visits have a ± 7 days window.

For analysis endpoints, the analysis visit will be re-mapped by the assessment time windows. In general, the summary tables will only be displayed by planned time points and visits, unless otherwise specified.

14.4. Appendix 4: Study Phases and Treatment Emergent Adverse Events

14.4.1. Study Phases

Assessments and events will be classified according to the time of occurrence relative to the start and/or stop date of the study treatment. The earliest and latest exposure treatment start and stop dates will be used to determine whether an assessment or event was pre-treatment, on-treatment or post-treatment. If it is not possible to tell whether an assessment or event was on-treatment or not it will be considered as on-treatment.

Study Phase	Definition
Pre-Treatment	Date \leq Study Treatment Start Date
On-Treatment	Study Treatment Start Date $<$ Date \leq Study Treatment Stop Date + 70 days
Post-Treatment	Date $>$ Study Treatment Stop Date + 70 days

NOTES:

- Time of study treatment dosing and assessments and events should be considered, if collected, then the study phases will be re-defined as following:
Pre-Treatment: Date $<$ Study Treatment Start Date
On-Treatment: Study Treatment Start Date \leq Date \leq Study Treatment Stop Date + 70 days
Post-Treatment: Date $>$ Study Treatment Stop Date + 70 days

Concomitant Medication start and end dates will be assigned to study time periods in relation to first dose of study treatment as defined below. The start date references time flag variables and end date reference time flag variables will be added to the concomitant medication datasets, respectively.

- **Start relative to treatment:** Assign to 'BEFORE' if start date is prior to study treatment start date or if subject has not taken any study treatment or (start date is missing and end date is before study treatment start date). Else assign to 'DURING' if the start date falls into the on-treatment period as defined above or if subject is ongoing (not all study treatment discontinuation records completed) or start date is missing. Else assign to 'AFTER' if start date is after the on-treatment period.
- **End relative to treatment:** Assign to 'BEFORE' if end date is prior to study treatment start date or if subject has not taken any study treatment. Else assign to 'DURING' if start date falls into the on-treatment period or if subject is ongoing (not all study treatment discontinuation records completed) or (end date is missing and start relative to treatment not 'AFTER'). Else assign to 'AFTER' if start date is after the on-treatment period or (end date is missing and start relative to treatment='AFTER').

Concomitant medication starts relative to treatment and end relative to treatment flags are used to select data to include in the Concomitant Medication summaries as follows:

- **Summary of Concomitant Medications:** This summary will contain medications including those with start date prior to study treatment start date and continue (missing end date or end date after study treatment start date) on therapy. Note that any medications with start date and end date prior to study treatment start date will be excluded. In addition, any medication that was started during post-therapy will be

excluded. Include concomitant medication records where start relative to treatment in ('BEFORE','DURING') and end relative to treatment in ('DURING','AFTER').

- Summary of Concomitant Medications with On-Therapy Onset: This summary will contain medications with start date after study treatment start date. In addition, any medication that was started during post-therapy (see above for definition of post-therapy) will be excluded. Include concomitant medication records where start relative to treatment in ('DURING') and end relative to treatment in ('DURING','AFTER').

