- 34. Belantamab mafodotin administration: Study drug administration ± 3 -day window.
- 35. Corneal management information:
 - a. Prophylactic preservative-free artificial tears must be administered in each eye at least 4-8 times daily beginning on Cycle 1 Day 1 until end of treatment.
 - b. At the start of each infusion, participants may apply cooling eye masks to their eyes for approximately 1 hour or as long as tolerated.
- 36. All related SAEs are to be collected from consent through PD follow-up.
- 37. Additional assessments may be conducted for those participants who experience a worsening in visual function. Participants who discontinue participation in the study will continue to be assessed during follow-up until resolution of visual symptoms. Continue to follow up with participants via telephone who are still experiencing visual symptoms even after discontinuation.

TMF-14065056 208465

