ocular AEs were keratopathy (71%, changes in corneal epithelium identified on eye exam, with or without symptoms), blurred vision (22%), and dry eye (13%). Decreased vision defined as Snellen score worse than 20/50 in the better seeing eye was reported in 18% of participants receiving belantamab mafodotin 2.5 mg/kg. Severe vision loss defined as 20/200 or worse in the better seeing eye was reported in 1% of participants receiving belantamab mafodotin 2.5 mg/kg.

The median time to onset of Grade 2 or above corneal findings (best corrected visual acuity or corneal examination) was 36 days (range: 19 to 143 days) in participants receiving belantamab mafodotin 2.5 mg/kg. The median time to resolution of these corneal findings was 91 days (range: 21 to 201 days).

Participants with history of dry eye were more prone to develop corneal examination findings. Therefore, active management of dry eye symptoms prior to and during treatment is recommended (*i.e.* administration of preservative-free artificial tears).

The ocular sub-study of DREAMM-2 provided no evidence that corticosteroid eye drops are beneficial in preventing or mitigating corneal events.

Infusion-related reactions

Infusion-related reactions (IRRs) are expected for biologic agents. In DREAMM-2 (data as of 31 Jan 2020), IRRs occurred in 21% of participants in the belantamab mafodotin 2.5 mg/kg, which were Grade 1 - 3 in severity. Most IRRs occurred with the first infusion and few participants experienced IRRs with subsequent infusions.

Although not protocol-mandated, pre-medications for IRR prophylaxis (including paracetamol, antihistamines, and steroids) were administered to 26%–27% of participants. One participant (2.5 mg/kg cohort) discontinued treatment due to IRRs (Grade 3 IRRs at first and second infusion).

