14.4.2. Treatment Emergent Flag for Adverse Events

Flag	Definition
Treatment Emergent	
• Study Treatment Start Date ≤ AE Start Date ≤ Study Treatment Stop Date + 70 days.

NOTES:

- If the study treatment stop date is missing, then the AE will be considered to be On-Treatment.
- Time of study treatment dosing and start/stop time of AEs should be considered, if collected.

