14.7.2.1. Handling of Missing and Partial Dates

Element	Reporting Detail
General	
 Partial dates will be displayed as captured in participant listing displays. Imputed partial dates will not be used to derive study day, duration (e.g. duration of adverse events), or elapsed time variables. In addition, imputed dates are not used for deriving the last contact date in the overall survival analysis dataset. Imputed dates will not be displayed in listings. However, where necessary, display macros may impute dates as temporary variables for the purpose of sorting data in listings only. In addition, partial dates may be imputed for 'slotting' data to study time periods or for specific analysis purposes as outlined below.
Adverse Events	
 The eCRF allows for the possibility of partial dates (i.e., only month and year) to be recorded for AE start and end dates; that is, the day of the month may be missing. 
 Missing Start Day: First of the month will be used unless this is before the start date of study treatment; in this case the study treatment start date will be used and hence the event is considered On-treatment as per Appendix 4: Study Phases and Treatment Emergent Adverse Events. Missing Stop Day: Last day of the month will be used. Completely missing start dates will remain missing, with no imputation applied. Consequently, time to onset and duration of such events will be missing. Completely missing end dates will remain missing, with no imputation applied. Consequently, duration of such events will be missing.
Concomitant Medications/Medical History	
 Partial dates for any concomitant medications recorded in the CRF will be imputed using the following convention: 
 If the partial date is a start date, a '01' will be used for the day and 'Jan' will be used for the month If the partial date is a stop date, a '28/29/30/31' will be used for the day (dependent on the month and year) and 'Dec' will be used for the month. The recorded partial date will be displayed in listings.
Covariates for efficacy analysis (Date of initial diagnosis/ Last recurrence/ Last progression)	
 If both month and day are missing, first of January will be used If only day is missing, first of the month will be used

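### The date-only study-phase table in SAP 14.4.1 leaves untimed Day 1 medication starts without a flag and puts untimed Day 1 blood products outside the on-therapy window

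*SAP*

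**What the plan says.** SAP 14.4.1 and the sections tied to it contain these rules:

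- **Fallback, above the table (14.4.1):** "If it is not possible to tell whether an assessment or event was on-treatment or not it will be considered as on-treatment".
- **Date-only table (14.4.1):** Pre-Treatment is "Date \leq Study Treatment Start Date". On-Treatment is "Study Treatment Start Date $<$ Date \leq Study Treatment Stop Date + 70 days".
- **Note under the table (14.4.1):** "Time of study treatment dosing and assessments and events should be considered, if collected, then the study phases will be re-defined as following". In the re-defined version the start date belongs to On-Treatment.
- **Treatment-emergent flag (14.4.2):** "Study Treatment Start Date ≤ AE Start Date ≤ Study Treatment Stop Date + 70 days". The start date is included whether or not a time exists.
- **Partial adverse event dates (14.7.2.1):** if imputing the first of the month would put the event before treatment, "the study treatment start date will be used and hence the event is considered On-treatment", with Appendix 4 given as the authority.
- **Medication start flag (14.4.1):** BEFORE needs a start date earlier than the treatment start date. DURING needs a start date in the on-treatment period, an ongoing participant, or a missing start date. AFTER needs a start date later than that period.
- **Medication summary filter (14.4.1):** a record needs a start flag of BEFORE or DURING and an end flag of DURING or AFTER.
- **SAP 6.6:** a medication is concomitant if it was used at any time in the on-treatment window. Blood products and blood supportive care products enter their tables by onset date within the on-therapy window.

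**The concern.** The first dosing day has two opposite classifications within one section, and the less suitable one applies by default when only dates are held. For adverse events the table conflicts with the treatment-emergent flag and, read alone, with the partial-date rule. For medications the effect is more concrete. The start flag combines a strict inequality from its own text with a strict inequality from the table, so the start date falls between the two.

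What is at stake is the content of three planned summaries: concomitant medications (Table 1.160), blood products (1.170) and blood supportive care products (1.180). Day 1 is a natural day for new medications, since the Schedule of Activities allows premedication then if needed.

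**Working it through.** The plan states no figure to reproduce. The check applies each rule, as written, to dates around the first dose. Day 1 is the treatment start date, and the participant has discontinued.

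**Step 1. Study phase against the treatment-emergent flag**

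| Event date | Date-only phase | Re-defined phase | Flag in 14.4.2 |
|---|---|---|---|
| Day before first dose | Pre | Pre | No |
| Day 1 | Pre | On | Yes |
| Day 2 | On | On | Yes |

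The date-only phase and the flag disagree on Day 1 and on neither neighbouring day.

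**Step 2. Start flag for a medication begun on Day 1, no clock time**

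- BEFORE: Day 1 is not earlier than Day 1. Fails.
- DURING: the date-only on-treatment period needs a date strictly after Day 1, the participant is not ongoing, and the start date is not missing. Fails.
- AFTER: Day 1 is not later than the stop date plus 70 days. Fails.

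No value is assigned. A medication begun on Day 2 gets DURING. So does one whose start date and end date are both missing, so a known Day 1 date is treated worse than no date.

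**Step 3. Through the summary filter**

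| Day 1 medication | Start / end flag, date-only | In summary? | Start / end flag, inclusive boundary | In summary? |
|---|---|---|---|---|
| Ends Day 1 | none / none | No | DURING / DURING | Yes |
| Ends later in treatment | none / none | No | DURING / DURING | Yes |
| No end date | none / DURING | No | DURING / DURING | Yes |

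**Step 4. Could another clause rescue the record?**

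- The ongoing-participant clause would assign DURING. SAP 3.2 places the final analysis after every participant has progressed, died, withdrawn, discontinued or been lost, so this clause should rarely apply.
- The note on collected times would move the boundary. Protocol 6.1.1 has infusion start and end times in the eCRF, but Protocol 6.5 asks for medication start and end dates and mentions no clock time.

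**Step 5. Blood products**

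Selection is by onset date in the on-therapy window. If that window is the date-only On-Treatment period, an untimed Day 1 onset lies outside it.

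**Step 6. Unit of effect**

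SAP 6.6 counts a participant once per ingredient. A participant disappears from a row only if no other use of that ingredient qualifies. One such participant moves the row by 1/6 = 16.7 percentage points with six treated, or 1/12 = 8.3 points with twelve. This is the weight of one participant, not an estimate of how many are affected.

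**The case against.** Five arguments can be made for the plan as it stands.

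1. **Adverse events have their own rule.** The 14.4.2 flag includes the start date. The partial-date rule cites Appendix 4 as a whole, which contains 14.4.2, and read against that section it is correct. Protocol 8.3.1 collects adverse events from the start of treatment and sends earlier occurrences to medical history. No adverse event table is said to select on study phase. This stands: no loss of adverse events is shown. SAP 8.2 does not, however, name the selector.
2. **The fallback sentence already makes undecidable cases on-treatment.** This stands only in part. The table gives an untimed Day 1 date a definite answer, the SAP does not say which prevails, and the medication flags have their own wording.
3. **Times may be collected, in which case the inclusive boundary applies.** The eCRF is not available to check. If medication and blood-product times are recorded, or if the note is meant to apply to all data because infusion times are held, the problem disappears.
4. **The prose shows the intent, and the data are listed.** SAP 6.6 and the description of the summary in 14.4.1 would include a Day 1 start; only the literal flags omit it. The listings of prior and concomitant medications, blood products and blood supportive care products show the records. This stands and limits the damage to summary counts. The on-therapy-onset medication summary is not among the planned tables.
5. **The boundary is deliberate.** SAP 5.2 assumes that untimed Day 1 assessments precede the first dose. That justifies the table for assessments, but not for events or medications.

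**Conclusion.** Wrong as written, minor. A literal program would omit untimed Day 1 medication starts from Table 1.160 in discontinued participants, and untimed Day 1 blood products and blood supportive care products from Tables 1.170 and 1.180, against the SAP's evident intent. The number of records cannot be given from the documents. The conclusion assumes that clock times are not held for these records, that the flags are programmed as worded, and that the on-therapy window in SAP 6.6 is the On-Treatment period of 14.4.1.

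A reader might infer two stronger claims, and the documents support neither:

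- **First-infusion reactions are lost from the safety tables.** Protocol 2.3.2 reports infusion-related reactions in 21% at 2.5 mg/kg in the phase II study and says "Most IRRs occurred with the first infusion". Applying that rate to the cohort counts expected reactions, not misclassified ones. Under the 14.4.2 flag none is misclassified. Misclassification would need a display that selects on study phase, and none is stated to.
- **Every participant's artificial-tears record is lost.** The Schedule of Activities says "Prophylactic preservative-free artificial tears must be administered in each eye at least 4-8 times daily beginning on Cycle 1 Day 1", but it lists the tears under study treatment. Whether they are captured as concomitant-medication records is not shown, so no 100% figure can be claimed.

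No dose decision, DLT count or efficacy result is affected.

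**What to change.** Amend the SAP as follows:

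- In 14.4.1, for adverse events, concomitant medications, blood products and blood supportive care products, define On-Treatment as start date ≤ date ≤ stop date + 70 days, whether or not time is collected. Use actual times where they exist. This is the boundary the SAP already gives in its note.
- For untimed assessments only, keep date ≤ start date as Pre-Treatment, in line with SAP 5.2. One inclusive rule for all data would make an untimed Day 1 laboratory value both baseline and On-Treatment.
- In the description of the on-therapy-onset medication summary, change the requirement from after the treatment start date to on or after it.
- In SAP 8.2, state that adverse event tables select on the 14.4.2 flag.

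The cost is SAP wording, with no new data. While editing, check one separate matter that this boundary does not cure: the end flag tests the start date, not the end date, for DURING and AFTER. In a discontinued participant, a medication begun before Day 1 with a known end date during treatment therefore gets no end flag under either boundary.
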